Appendix 2: Drugs With A Risk Of Torsades De Pointes

Generic Name	Brand Name	Class/Clinical Use	Comments
		rhythm	
Quinidine	Cardioquin®	Anti-arrhythmic / abnormal heart rhythm	Females>Males
Quinidine	Quinaglute®	Anti-arrhythmic / abnormal heart rhythm	Females>Males
Sotalol	Betapace®	Anti-arrhythmic / abnormal heart rhythm	Females>Males
Sparfloxacin	Zagam®	Antibiotic / bacterial infection	
Thioridazine	Mellaril®	Anti-psychotic / schizophrenia	
Vandetanib	Caprelsa®	Anti-cancer / Thyroid cancer	
Fluconazole	Diflucan®	Anti-arrhythmic / abnormal heart rhythm	
Ciprofloxacin	Ciloxan, Cipro, Neofloxin	Anti-arrhythmic / abnormal heart rhythm	

Appendix 3: Drug Diaries

PLX3397 QD - Patient Drug Diary – Phase Ib, Cycle # _____

CC#12751: Enhancing Efficacy of Chemotherapy in Triple Negative/Basal-Like Breast Cancer by Targeting Macrophages: A Phase Ib/II study of PLX 3397 and Eribulin in Patients with Metastatic Breast Cancer

Study Subject ID #: _____ **Patient Name:** _____

Current Assigned dose: _____ **Start Date:** _____

Reminders:

- Study medication should be stored at room temperature (Temperature storage range 15-30 °C or 59-86 °F).
- Take your dose of study medication every 24 hours (± 2 hours) If it is after 2 hours from when your dose was due, skip that dose and continue with the subsequent dose. Fast for at least 1 hour prior to taking the study medication and 1 hour after you take the study medication. You are allowed to have a low-fat, bland snack (crackers, toast, tea, etc.) if needed (if you are feeling nauseous or weak) during this 2 hour period.
- Medication should be taken with at least 8 ounces (1 cup) of room temperature water.
- Missed doses should be skipped and not taken as a double dose at the next dosing timepoint. If you vomit your dose, you should not make-up that dose or take extra study drug at the next dosing timepoint.
- Write down the time each dose is taken.
- Bring your study medication and study diary with you every time you visit the clinic.
- Contact your study doctor if you have any questions/concerns.

Patient Signature: _____

Cycle #	Day	Date mm/dd/yyyy	Time of Dose	Were you fasting before and after to your dose?(circle one)		# of capsules taken	Reason for missed dose
				Before: Yes/No	After: Yes/No		
Cycle _____	Day 1*	/ /		Before: Yes/No	After: Yes/No		
Cycle _____	Day 2**	/ /		Before: Yes/No	After: Yes/No		
Cycle _____	Day 3	/ /		Before: Yes/No	After: Yes/No		
Cycle _____	Day 4	/ /		Before: Yes/No	After: Yes/No		
Cycle _____	Day 5	/ /		Before: Yes/No	After: Yes/No		
Cycle _____	Day 6	/ /		Before: Yes/No	After: Yes/No		
Cycle _____	Day 7	/ /		Before: Yes/No	After: Yes/No		
Cycle _____	Day 8	/ /		Before: Yes/No	After: Yes/No		
Cycle _____	Day 9	/ /		Before: Yes/No	After: Yes/No		
Cycle _____	Day 10	/ /		Before: Yes/No	After: Yes/No		
Cycle _____	Day 11	/ /		Before: Yes/No	After: Yes/No		
Cycle _____	Day 12	/ /		Before: Yes/No	After: Yes/No		

PLX3397 QD - Patient Drug Diary – Phase Ib, Cycle # _____

CC#12751: Enhancing Efficacy of Chemotherapy in Triple Negative/Basal-Like Breast Cancer by Targeting Macrophages: A Phase Ib/II study of PLX 3397 and Eribulin in Patients with Metastatic Breast Cancer

Study Subject ID #: _____ **Patient Name:** _____

Current Assigned dose: _____ **Start Date:** _____

Reminders:

- Study medication should be stored at room temperature (Temperature storage range 15-30 °C or 59-86 °F).
- Take your dose of study medication every 24 hours (± 2 hours) If it is after 2 hours from when your dose was due, skip that dose and continue with the subsequent dose. Fast for at least 1 hour prior to taking the study medication and 1 hour after you take the study medication. You are allowed to have a low-fat, bland snack (crackers, toast, tea, etc.) if needed (if you are feeling nauseous or weak) during this 2 hour period.
- Medication should be taken with at least 8 ounces (1 cup) of room temperature water.
- Missed doses should be skipped and not taken as a double dose at the next dosing timepoint. If you vomit your dose, you should not make-up that dose or take extra study drug at the next dosing timepoint.
- Write down the time each dose is taken.
- Bring your study medication and study diary with you every time you visit the clinic.
- Contact your study doctor if you have any questions/concerns.

Patient Signature: _____

Cycle #	Day	Date mm/dd/yyyy	Time of Dose	Were you fasting before and after to your dose?(circle one)		# of capsules taken	Reason for missed dose
				Before: Yes/No	After: Yes/No		
Cycle ____	Day 13	/ /		Before: Yes/No	After: Yes/No		
Cycle ____	Day 14	/ /		Before: Yes/No	After: Yes/No		
Cycle ____	Day 15	/ /		Before: Yes/No	After: Yes/No		
Cycle ____	Day 16	/ /		Before: Yes/No	After: Yes/No		
Cycle ____	Day 17	/ /		Before: Yes/No	After: Yes/No		
Cycle ____	Day 18	/ /		Before: Yes/No	After: Yes/No		
Cycle ____	Day 19	/ /		Before: Yes/No	After: Yes/No		
Cycle ____	Day 20	/ /		Before: Yes/No	After: Yes/No		
Cycle ____	Day 21	/ /		Before: Yes/No	After: Yes/No		

* For Cycle 1 and Cycle 2, Day 1, do not take your morning dose of PLX3397 until you are instructed to do so during your clinic visit.

** For Day 2 of Cycle 1 ONLY, do not take your morning dose of PLX3397 until you are instructed to do so during your clinic visit.

PLX3397 BID - Patient Drug Diary – Phase Ib, Cycle # _____

CC#12751: Enhancing Efficacy of Chemotherapy in Triple Negative/Basal-Like Breast Cancer by Targeting Macrophages: A Phase Ib/II study of PLX 3397 and Eribulin in Patients with Metastatic Breast Cancer

Study Subject ID #: _____ **Patient Name:** _____

Current Assigned dose: _____ **Start Date:** _____

Reminders:

- Study medication should be stored at room temperature (Temperature storage range 15-30 °C or 59-86 °F).
- Take your dose of study medication every 12 hours (± 2 hours). If it is after 2 hours from when your dose was due, skip that dose and continue with your next scheduled dose.
- Fast for at least 1 hour prior to taking the study medication and 1 hour after you take the study medication. You are allowed to have a low-fat, bland snack (crackers, toast, tea, etc.) if needed (if you are feeling nauseous or weak) during this 2 hour period.
- Medication should be taken with at least 8 ounces (1 cup) of room temperature water.
- Missed doses should be skipped and not taken as a double dose at the next dosing timepoint. If you vomit your dose, you should not make-up that dose or take extra study drug at the next dosing timepoint.
- Write down the time each dose is taken.
- Bring your study medication and study diary with you every time you visit the clinic.
- Contact your study doctor if you have any questions/concerns.

Patient Signature: _____

Cycle #	Day	Date mm/dd/yyyy	Time of Dose**	Were you fasting before and after to your dose?(circle one)		# of capsule s taken	Reason for missed dose
				Before: Yes/No	After: Yes/No		
Cycle _____	Day 1*		: AM	Before: Yes/No	After: Yes/No		
Cycle _____	Day 1	/ /	: PM	Before: Yes/No	After: Yes/No		
Cycle _____	Day 2**	/ /	: AM	Before: Yes/No	After: Yes/No		
Cycle _____	Day 2	/ /	: PM	Before: Yes/No	After: Yes/No		
Cycle _____	Day 3	/ /	: AM	Before: Yes/No	After: Yes/No		
Cycle _____	Day 3	/ /	: PM	Before: Yes/No	After: Yes/No		
Cycle _____	Day 4	/ /	: AM	Before: Yes/No	After: Yes/No		
Cycle _____	Day 4	/ /	: PM	Before: Yes/No	After: Yes/No		
Cycle _____	Day 5	/ /	: AM	Before: Yes/No	After: Yes/No		
Cycle _____	Day 5	/ /	: PM	Before: Yes/No	After: Yes/No		
Cycle _____	Day 6	/ /	: AM	Before: Yes/No	After: Yes/No		
Cycle _____	Day 6	/ /	: PM	Before: Yes/No	After: Yes/No		
Cycle _____	Day 7	/ /	: AM	Before: Yes/No	After: Yes/No		
Cycle _____	Day 7	/ /	: PM	Before: Yes/No	After: Yes/No		

Study Subject ID #: _____ Patient Name: _____

Current Assigned dose: _____ Start Date: _____

Reminders:

- Study medication should be stored at room temperature (Temperature storage range 15-30 °C or 59-86 °F).
- Take your dose of study medication every 12 hours (± 2 hours). If it is after 2 hours from when your dose was due, skip that dose and continue with your next scheduled dose.
- Fast for at least 1 hour prior to taking the study medication and 1 hour after you take the study medication. You are allowed to have a low-fat, bland snack (crackers, toast, tea, etc.) if needed (if you are feeling nauseous or weak) during this 2 hour period.
- Medication should be taken with at least 8 ounces (1 cup) of room temperature water.
- Missed doses should be skipped and not taken as a double dose at the next dosing timepoint. If you vomit your dose, you should not make-up that dose or take extra study drug at the next dosing timepoint.
- Write down the time each dose is taken.
- Bring your study medication and study diary with you every time you visit the clinic.
- Contact your study doctor if you have any questions/concerns.

Patient Signature: _____

Cycle #	Day	Date mm/dd/yyyy	Time of Dose**	Were you fasting before and after to your dose?(circle one)		# of capsule s taken	Reason for missed dose
				Before: Yes/No	After: Yes/No		
Cycle__	Day 8	/ /	: AM	Before: Yes/No	After: Yes/No		
Cycle__	Day 8	/ /	: PM	Before: Yes/No	After: Yes/No		
Cycle__	Day 9	/ /	: AM	Before: Yes/No	After: Yes/No		
Cycle__	Day 9	/ /	: PM	Before: Yes/No	After: Yes/No		
Cycle__	Day 10	/ /	: AM	Before: Yes/No	After: Yes/No		
Cycle__	Day 10	/ /	: PM	Before: Yes/No	After: Yes/No		
Cycle__	Day 11	/ /	: AM	Before: Yes/No	After: Yes/No		
Cycle__	Day 11	/ /	: PM	Before: Yes/No	After: Yes/No		
Cycle__	Day 12	/ /	: AM	Before: Yes/No	After: Yes/No		
Cycle__	Day 12	/ /	: PM	Before: Yes/No	After: Yes/No		
Cycle__	Day 13	/ /	: AM	Before: Yes/No	After: Yes/No		
Cycle__	Day 13	/ /	: PM	Before: Yes/No	After: Yes/No		
Cycle__	Day 14	/ /	: AM	Before: Yes/No	After: Yes/No		
Cycle__	Day 14	/ /	: PM	Before: Yes/No	After: Yes/No		
Cycle__	Day 15	/ /	: AM	Before: Yes/No	After: Yes/No		
Cycle__	Day 15	/ /	: PM	Before: Yes/No	After: Yes/No		

Study Subject ID #: _____ Patient Name: _____

Current Assigned dose: _____ Start Date: _____

Reminders:

- Study medication should be stored at room temperature (Temperature storage range 15-30 °C or 59-86 °F).
- Take your dose of study medication every 12 hours (± 2 hours). If it is after 2 hours from when your dose was due, skip that dose and continue with your next scheduled dose.
- Fast for at least 1 hour prior to taking the study medication and 1 hour after you take the study medication. You are allowed to have a low-fat, bland snack (crackers, toast, tea, etc.) if needed (if you are feeling nauseous or weak) during this 2 hour period.
- Medication should be taken with at least 8 ounces (1 cup) of room temperature water.
- Missed doses should be skipped and not taken as a double dose at the next dosing timepoint. If you vomit your dose, you should not make-up that dose or take extra study drug at the next dosing timepoint.
- Write down the time each dose is taken.
- Bring your study medication and study diary with you every time you visit the clinic.
- Contact your study doctor if you have any questions/concerns.

Patient Signature: _____

Cycle #	Day	Date mm/dd/yyyy	Time of Dose**	Were you fasting before and after to your dose?(circle one)		# of capsule s taken	Reason for missed dose
				Before: Yes/No	After: Yes/No		
Cycle__	Day 16	/ /	: AM	Before: Yes/No	After: Yes/No		
Cycle__	Day 16	/ /	: PM	Before: Yes/No	After: Yes/No		
Cycle__	Day 17	/ /	: AM	Before: Yes/No	After: Yes/No		
Cycle__	Day 17	/ /	: PM	Before: Yes/No	After: Yes/No		
Cycle__	Day 18	/ /	: AM	Before: Yes/No	After: Yes/No		
Cycle__	Day 18	/ /	: PM	Before: Yes/No	After: Yes/No		
Cycle__	Day 19	/ /	: AM	Before: Yes/No	After: Yes/No		
Cycle__	Day 19	/ /	: PM	Before: Yes/No	After: Yes/No		
Cycle__	Day 20	/ /	: AM	Before: Yes/No	After: Yes/No		
Cycle__	Day 20	/ /	: PM	Before: Yes/No	After: Yes/No		
Cycle__	Day 21	/ /	: AM	Before: Yes/No	After: Yes/No		
Cycle__	Day 21	/ /	: PM	Before: Yes/No	After: Yes/No		

*For Cycle 1 and Cycle 2, Day 1, do not take your morning dose of PLX3397 until you are instructed to do so during your clinic visit.

**For Day 2 of Cycle 1 ONLY, do not take your morning dose of PLX3397 until you are instructed to do so during your clinic visit.

PLX3397 BID - Patient Drug Diary – Phase II, Cycle # _____

CC#12751: Enhancing Efficacy of Chemotherapy in Triple Negative/Basal-Like Breast Cancer by Targeting Macrophages: A Phase Ib/II study of PLX 3397 and Eribulin in Patients with Metastatic Breast Cancer

Study Subject ID #: _____ **Patient Name:** _____

Current Assigned dose: _____ **Start Date:** _____

Reminders:

- Study medication should be stored at room temperature (Temperature storage range 15-30 °C or 59-86 °F).
- Take your dose of study medication every 12 hours (± 2 hours). If it is after 2 hours from when your dose was due, skip that dose and continue with your next scheduled dose.
- **Take your study medication daily for 5 days, followed by 2 days off, then restart each week with the same schedule**
- Fast for at least 1 hour prior to taking the study medication and 1 hour after you take the study medication. You are allowed to have a low-fat, bland snack (crackers, toast, tea, etc.) if needed (if you are feeling nauseous or weak) during this 2 hour period.
- Medication should be taken with at least 8 ounces (1 cup) of room temperature water.
- Missed doses should be skipped and not taken as a double dose at the next dosing timepoint. If you vomit your dose, you should not make-up that dose or take extra study drug at the next dosing timepoint. If you miss or hold a dose, maintain the 5 days on/2 days off schedule marked on the study calendar.
- Write down the time each dose is taken.
- Bring your study medication and study diary with you every time you visit the clinic.
- Contact your study doctor if you have any questions/concerns.

Patient Signature: _____

Cycle #	Day	Date mm/dd/yyyy	Time of Dose	Were you fasting before and after to your dose? (circle one)	# of capsules taken	Reason for missed dose
In Cycle 1, you will start taking PLX3397 six to seven days before starting eribulin.						
Cycle 1	Day -7		: AM	Before: Yes/No	After: Yes/No	
Cycle 1	Day-7	/ /	: PM	Before: Yes/No	After: Yes/No	
Cycle 1	Day-6	/ /	: AM	Before: Yes/No	After: Yes/No	
Cycle 1	Day-6	/ /	: PM	Before: Yes/No	After: Yes/No	
Cycle 1	Day-5	/ /	: AM	Before: Yes/No	After: Yes/No	
Cycle 1	Day-5	/ /	: PM	Before: Yes/No	After: Yes/No	
Cycle 1	Day-4	/ /	: AM	Before: Yes/No	After: Yes/No	
Cycle 1	Day-4	/ /	: PM	Before: Yes/No	After: Yes/No	
Cycle 1	Day-3	/ /	: AM	Before: Yes/No	After: Yes/No	
Cycle 1	Day-3	/ /	: PM	Before: Yes/No	After: Yes/No	
Cycle 1	Day-2	/ /	DO NOT TAKE STUDY DRUG			
Cycle 1	Day-2	/ /	DO NOT TAKE STUDY DRUG			

Study Subject ID #: _____ Patient Name: _____

Current Assigned dose: _____ Start Date: _____

Reminders:

- Study medication should be stored at room temperature (Temperature storage range 15-30 °C or 59-86 °F).
- Take your dose of study medication every 12 hours (± 2 hours). If it is after 2 hours from when your dose was due, skip that dose and continue with your next scheduled dose.
- **Take your study medication daily for 5 days, followed by 2 days off, then restart each week with the same schedule**
- Fast for at least 1 hour prior to taking the study medication and 1 hour after you take the study medication. You are allowed to have a low-fat, bland snack (crackers, toast, tea, etc.) if needed (if you are feeling nauseous or weak) during this 2 hour period.
- Medication should be taken with at least 8 ounces (1 cup) of room temperature water.
- Missed doses should be skipped and not taken as a double dose at the next dosing timepoint. If you vomit your dose, you should not make-up that dose or take extra study drug at the next dosing timepoint. If you miss or hold a dose, maintain the 5 days on/2 days off schedule marked on the study calendar.
- Write down the time each dose is taken.
- Bring your study medication and study diary with you every time you visit the clinic.
- Contact your study doctor if you have any questions/concerns.

Patient Signature: _____

Cycle #	Day	Date mm/dd/yyyy	Time of Dose	Were you fasting before and after to your dose? (circle one)		# of capsules taken	Reason for missed dose
Cycle 1	Day-1	/ /	DO NOT TAKE STUDY DRUG				
Cycle 1	Day-1	/ /	DO NOT TAKE STUDY DRUG				
Cycle__	Day 1	/ /	: AM	Before: Yes/No	After: Yes/No		
Cycle__	Day 1	/ /	: PM	Before: Yes/No	After: Yes/No		
Cycle__	Day 2	/ /	: AM	Before: Yes/No	After: Yes/No		
Cycle__	Day 2	/ /	: PM	Before: Yes/No	After: Yes/No		
Cycle__	Day 3	/ /	: AM	Before: Yes/No	After: Yes/No		
Cycle__	Day 3	/ /	: PM	Before: Yes/No	After: Yes/No		
Cycle__	Day 4	/ /	: AM	Before: Yes/No	After: Yes/No		
Cycle__	Day 4	/ /	: PM	Before: Yes/No	After: Yes/No		
Cycle__	Day 5	/ /	: AM	Before: Yes/No	After: Yes/No		
Cycle__	Day 5	/ /	: PM	Before: Yes/No	After: Yes/No		
Cycle__	Day 6	/ /	DO NOT TAKE STUDY DRUG				
Cycle__	Day 6	/ /	DO NOT TAKE STUDY DRUG				
Cycle__	Day 7	/ /	DO NOT TAKE STUDY DRUG				

Study Subject ID #: _____ Patient Name: _____

Current Assigned dose: _____ Start Date: _____

Reminders:

- Study medication should be stored at room temperature (Temperature storage range 15-30 °C or 59-86 °F).
- Take your dose of study medication every 12 hours (± 2 hours). If it is after 2 hours from when your dose was due, skip that dose and continue with your next scheduled dose.
- **Take your study medication daily for 5 days, followed by 2 days off, then restart each week with the same schedule**
- Fast for at least 1 hour prior to taking the study medication and 1 hour after you take the study medication. You are allowed to have a low-fat, bland snack (crackers, toast, tea, etc.) if needed (if you are feeling nauseous or weak) during this 2 hour period.
- Medication should be taken with at least 8 ounces (1 cup) of room temperature water.
- Missed doses should be skipped and not taken as a double dose at the next dosing timepoint. If you vomit your dose, you should not make-up that dose or take extra study drug at the next dosing timepoint. If you miss or hold a dose, maintain the 5 days on/2 days off schedule marked on the study calendar.
- Write down the time each dose is taken.
- Bring your study medication and study diary with you every time you visit the clinic.
- Contact your study doctor if you have any questions/concerns.

Patient Signature: _____

Cycle #	Day	Date mm/dd/yyyy	Time of Dose	Were you fasting before and after to your dose? (circle one)		# of capsules taken	Reason for missed dose
				Before: Yes/No	After: Yes/No		
Cycle ___	Day 7	/ /	DO NOT TAKE STUDY DRUG				
Cycle ___	Day 8	/ /	: AM	Before: Yes/No	After: Yes/No		
Cycle ___	Day 8	/ /	: PM	Before: Yes/No	After: Yes/No		
Cycle ___	Day 9	/ /	: AM	Before: Yes/No	After: Yes/No		
Cycle ___	Day 9	/ /	: PM	Before: Yes/No	After: Yes/No		
Cycle ___	Day 10	/ /	: AM	Before: Yes/No	After: Yes/No		
Cycle ___	Day 10	/ /	: PM	Before: Yes/No	After: Yes/No		
Cycle ___	Day 11	/ /	: AM	Before: Yes/No	After: Yes/No		
Cycle ___	Day 11	/ /	: PM	Before: Yes/No	After: Yes/No		
Cycle ___	Day 12	/ /	: AM	Before: Yes/No	After: Yes/No		
Cycle ___	Day 12	/ /	: PM	Before: Yes/No	After: Yes/No		
Cycle ___	Day 13	/ /	DO NOT TAKE STUDY DRUG				
Cycle ___	Day 13	/ /	DO NOT TAKE STUDY DRUG				
Cycle ___	Day 14	/ /	DO NOT TAKE STUDY DRUG				
Cycle ___	Day 14	/ /	DO NOT TAKE STUDY DRUG				

Study Subject ID #: _____ Patient Name: _____

Current Assigned dose: _____ Start Date: _____

Reminders:

- Study medication should be stored at room temperature (Temperature storage range 15-30 °C or 59-86 °F).
- Take your dose of study medication every 12 hours (± 2 hours). If it is after 2 hours from when your dose was due, skip that dose and continue with your next scheduled dose.
- **Take your study medication daily for 5 days, followed by 2 days off, then restart each week with the same schedule**
- Fast for at least 1 hour prior to taking the study medication and 1 hour after you take the study medication. You are allowed to have a low-fat, bland snack (crackers, toast, tea, etc.) if needed (if you are feeling nauseous or weak) during this 2 hour period.
- Medication should be taken with at least 8 ounces (1 cup) of room temperature water.
- Missed doses should be skipped and not taken as a double dose at the next dosing timepoint. If you vomit your dose, you should not make-up that dose or take extra study drug at the next dosing timepoint. If you miss or hold a dose, maintain the 5 days on/2 days off schedule marked on the study calendar.
- Write down the time each dose is taken.
- Bring your study medication and study diary with you every time you visit the clinic.
- Contact your study doctor if you have any questions/concerns.

Patient Signature: _____

Cycle #	Day	Date mm/dd/yyyy	Time of Dose	Were you fasting before and after to your dose? (circle one)		# of capsules taken	Reason for missed dose
				Before: Yes/No	After: Yes/No		
Cycle ___	Day 15	/ /	: AM	Before: Yes/No	After: Yes/No		
Cycle ___	Day 15	/ /	: PM	Before: Yes/No	After: Yes/No		
Cycle ___	Day 16	/ /	: AM	Before: Yes/No	After: Yes/No		
Cycle ___	Day 16	/ /	: PM	Before: Yes/No	After: Yes/No		
Cycle ___	Day 17	/ /	: AM	Before: Yes/No	After: Yes/No		
Cycle ___	Day 17	/ /	: PM	Before: Yes/No	After: Yes/No		
Cycle ___	Day 18	/ /	: AM	Before: Yes/No	After: Yes/No		
Cycle ___	Day 18	/ /	: PM	Before: Yes/No	After: Yes/No		
Cycle ___	Day 19	/ /	: AM	Before: Yes/No	After: Yes/No		
Cycle ___	Day 19	/ /	: PM	Before: Yes/No	After: Yes/No		
Cycle ___	Day 20	/ /	DO NOT TAKE STUDY DRUG				
Cycle ___	Day 20	/ /	DO NOT TAKE STUDY DRUG				
Cycle ___	Day 21	/ /	DO NOT TAKE STUDY DRUG				
Cycle ___	Day 21	/ /	DO NOT TAKE STUDY DRUG

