3.1.2 Phase II

The phase II portion of this trial will evaluate PFS in patients with TNBC treated with PLX3397 and eribulin, using the dose of PLX3397 determined in the phase Ib study in a two-step design. Please see the statistical section for details regarding enrollment and statistical design. Treatment is preceded by a 6 to 7 day lead-in phase, in which patients will take PLX3397 800mg (400 mg in the morning and 400 mg at night) for 5 days, followed by 1 to 2 days off before starting eribulin combined with PLX3397. PLX3397 will continue to be given on a 5 days on, 2 days off schedule, repeated weekly, throughout the course of treatment. Patients with accessible

tumor will undergo a core biopsy of tumor before the start of PLX3397 treatment, and then a fine needle aspiration or core biopsy will be performed on the day of or the day before the start of eribulin (day -2 to day 0).

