Due to the bone marrow suppression known to occur with eribulin, patients may receive myeloid growth factors at any time, at physician discretion (for guidelines regarding use of neupogen, see section 6.1). An eribulin premedication regimen of intravenous dexamethasone (6 mg, or physician-selected dose), or other equivalent steroid, <60 minutes prior to eribulin. This may be tapered with subsequent doses per investigator discretion.

Note: Patients enrolled on to the trial under protocol version 6.0 which allowed for Eribulin dosing schedule of Day 1 and Day 15 every 28 days will remain on that treatment and assessment schedule.

Phase II: The phase II portion will begin after the MTD for PLX3397 is determined and we will enroll a total of 56 patients with triple (ER/PR/HER2) negative metastatic breast cancer to evaluate the safety and efficacy of the proposed treatment. In the phase II study, treatment is preceded by a 6 to 7 day lead-in phase, in which patients will take PLX3397 800mg (400 mg in the morning and 400 mg at night) alone for 5 days, followed by 1 to 2 days off before starting eribulin combined with PLX3397. PLX3397 will continue to be given on a 5 days on, 2 days off schedule, repeated weekly, throughout the course of treatment. Concomitant antihistamines are recommended to reduce the incidence of rash. A tumor core biopsy will be obtained before treatment start, and then again before the start of eribulin. Patients will be treated until clinical or radiographic disease progression or cumulative toxicity and will be evaluated regularly in clinic. Evaluation of disease response or progression will be accomplished with CT scans, and bone scans as indicated, every 6 weeks. Visits will take place before each dose of eribulin (Day 1 and Day 8) during cycle 1, and then on Day 1 before cycle 2 and beyond.

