Informed Consent		X												
Registration			X											
History & Exam			X		X	X		X			X			X
ECOG			X		X	X		X			X			
ConMed Review			X		X	X		X	X		X	X		X
Peripheral Neuropathy		X			X			X			X			
CBC w/ 5 part diff.			X		X	X		X	X		X	X		X
Chemistry Panel	BUN, CO2, Cl, K, Na, Creatinine, Glucose (non- fasting), & Magnesium		X		X			X			X			X
Liver Function Tests	ALT, AST, AlkPhos, Total Bilirubin, & Albumin		X		X	X	X ¹⁰	X	X	X ¹⁰	X	X	X ¹⁰	X
PT/PTT ¹¹	Completed prior to tumor biopsy		X											
Pregnancy Test ²	Within 7 days of beginning treatment		X								X			
EKG ³		X						X						
Eribulin Therapy, IV ⁴	Day 1 & 8, q 21 days				X	X ⁵		X	X		X	X		
PLX3397 Therapy	Oral				Beginning With Lead-In Phase (Day -7 to -6): Daily (self-administered)									
Bone Scan & other imaging	Baseline, then as indicated	X												
CT (C/A/P)	Every 6 weeks ⁹	X									X			X
Blood for CSF1 ⁶				X	X			X			X ⁸			
Blood for Leukocyte Subtyping ⁶				X	X			X			X ⁸			
Tumor biopsy	Required for patients w/ accessible tumor		X		X (Day 0/ -1)									
Archived Tumor Tissue	Requested of all participants		X											

1. Allowed a window of ± 3 days for Day 1 procedures
2. In women of child bearing potential. Urine or Serum test allowed.
3. EKGs performed at the start of every other cycle (even numbered), at 6 week intervals
4. The following eribulin treatment delays are allowed for **patient coordination**:
C1 D8 (up to 3 days), C2+ D1 (up to 14 days), and C2+ D8 (up to 3 days)
5. A delay in C1 D8 of up to 7 days is allowed for resolution of toxicity

6. *Blood should be drawn before the first dose of PLX3397 during the lead-in phase, and before each administration of eribulin.*
7. *EOT procedures should occur within 30 days of last dose, after which the patient will be Off-Study.*
8. *Cycle 4 Day 1 only*
9. *Patients with either CR or PR and who have received at least 6 cycles of therapy may reduce the frequency of scans to every 9 weeks.*
10. *Liver function tests will be completed on D15 of the first three cycles only (C1D15, C2D15, and C3D15).*
11. *PT/PTT is only required for patients getting visceral organ biopsies*

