11.2 PLX3397

11.2.1 PLX3397 Administration

PLX3397 will be administered orally using a capsule formulation (200 mg per capsule). PLX3397 will be administered only to patients who have signed and dated an informed consent form. PLX3397 will be administered on a 5 day on, 2 day off schedule, repeated weekly, beginning C1D1 (baseline) for Phase Ib, or Day -7/-6 for Phase II. PLX3397 should be taken orally with 240 mL (8 oz) of room-temperature water in the fasting state. **The patient should fast at least 1 hour before administration and 1 hour after administration of PLX3397.** Patients will be permitted to eat a low-fat, bland snack (e.g., crackers, toast, tea) during the fasting period if needed. PLX3397 should be taken by the patient at approximately the same time of day.

Instructions for BID Dosing:

The time between BID doses should be approximately 12 hrs. Dosing may occur once daily (QD) under certain circumstances (e.g. dose reductions) and at the discretion of the Investigator in consultation with the Principal Investigator.

On C1D1, C1D2 and C2D1, the patients should take the morning dose of PLX3397 at the clinical site after the pre-dose PK blood sample is obtained— patients should be instructed not to take the study drug at home prior to these clinic visits. The time of dosing will be recorded in the clinic. The evening dose of PLX3397 should be taken by the patient at home. On all other visit days, patients may administer the study drug at home and record dosing information in the PLX3397 administration diary.

Missed doses of greater than 2 hrs before or after the appropriate dosing time should be skipped and not taken as a double dose at the next dosing timepoint. For example, a patient who takes their PLX3397 at 8 a.m. and 8 p.m. each day should not take their dose if they are outside of the ± 2 hr window period.

Patients who vomit their dose should be instructed to NOT make up that dose.

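### In its own day numbering, the only Phase II diary grid fits a Day -7 lead-in start: a patient who starts on the permitted Day -6 and follows the rows would take 4 dosing days, not the required 5

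*Combined protocol and SAP*

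**What the plan says.** Section 3.1.2 gives the Phase II lead-in as PLX3397 400 mg twice daily "for 5 days, followed by 1 to 2 days off before starting eribulin combined with PLX3397". Section 5.1 states the same rule: "alone for 5 days, followed by 1 to 2 days off before starting eribulin combined with PLX3397". In both, the number of dosing days is fixed at 5. Only the number of days off varies, which is why the lead-in lasts 6 or 7 days.

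The start day may be Day -7 or Day -6. Table 8-2 and section 8.2.1 show both, and section 11.2.1 gives a "5 day on, 2 day off schedule, repeated weekly, beginning C1D1 (baseline) for Phase Ib, or Day -7/-6 for Phase II".

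Appendix 3 holds one Phase II diary; the other diaries there are for Phase Ib. The Phase II diary tells the patient: "In Cycle 1, you will start taking PLX3397 six to seven days before starting eribulin". Its lead-in grid has morning and evening dosing rows for Days -7, -6, -5, -4 and -3. The rows for Days -2 and -1 read "DO NOT TAKE STUDY DRUG", and the next row is Day 1. There is no second layout and no footnote for a Day -6 start. A bold reminder on the same page says: "Take your study medication daily for 5 days, followed by 2 days off, then restart each week with the same schedule".

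**The concern.** A diary is an operative instruction: the patient takes the drug at home and fills in the rows. For a Day -7 start the printed rows agree with sections 3.1.2 and 5.1. For a Day -6 start they do not, because the grid fixes the last dosing day at Day -3 whichever day the patient began. Followed literally, the form would give less lead-in drug than the protocol requires, on a start day that the protocol allows.

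The lead-in exists to show what PLX3397 does alone to serum CSF1, blood leukocytes and, where biopsies are repeated, tumor tissue before eribulin (sections 14.6 and 14.6.2). If some patients had 4 dosing days and others 5, exposure before the second sample would differ between patients for no scientific reason.

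**Working it through.** Inputs:

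- Daily lead-in dose 800 mg (sections 3.1.2 and 5.1).
- Capsule strength 200 mg (section 11.2.1), so 800 / 200 = 4 capsules per day.
- Required lead-in: 5 dosing days, then 1 to 2 days off (sections 3.1.2 and 5.1).
- Printed grid: drug on Days -7 to -3, no drug on Days -2 and -1, then Day 1, with no Day 0 row (Appendix 3).

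Method: count the dosing rows from the start day to Day -1, then multiply by 800 mg. The Day -7 line comes first, as a check that the grid reproduces the protocol's own figure.

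| Case | Days on | Days off | Lead-in length | Dose | Capsules |
|---|---|---|---|---|---|
| Day -7 start, printed grid | Days -7 to -3 = 5 | 2 | 7 days | 5 × 800 = 4000 mg | 5 × 4 = 20 |
| Day -6 start, printed grid | Days -6 to -3 = 4 | 2 | 6 days | 4 × 800 = 3200 mg | 4 × 4 = 16 |
| Day -6 start, rule in 3.1.2 and 5.1 | Days -6 to -2 = 5 | 1 | 6 days | 5 × 800 = 4000 mg | 5 × 4 = 20 |

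The shortfall for a Day -6 starter who follows the labels is 4000 - 3200 = 800 mg, and 800 / 4000 = 20%. It is one dosing day, Day -2. The 2 days off that the grid gives are within the permitted 1 to 2, so only the number of dosing days is wrong.

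Re-dating the rows does not fully cure this. The grid has 5 + 2 = 7 lead-in days and a Day -6 start has 6. If the patient writes the first dose against the first row, all 5 dosing days are kept, but the second no-drug day then falls on the date of Day 1, when combined treatment begins. Staff would have to strike out a row as well as change dates.

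The count depends on the day numbering. Without a Day 0, Days -7 and -6 are 7 and 6 days before Day 1, which matches the stated 6 to 7 day lead-in. If a separate Day 0 precedes Day 1, they are 8 and 7 days before it, and a Day -7 start falls outside that range. In that case a protocol Day -6 start is 7 calendar days before Day 1. That corresponds to the first row of the diary, the one labelled Day -7, and gives 5 dosing days and 2 off.

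**The case against.** The strongest reply is that the path to an error is narrow. The bold reminder says five days of drug. The date fields are blank, so a patient who begins at the first row takes five days. Blood is drawn before the first lead-in dose (Table 8-2, note 6), so staff see the patient at the start and can mark the diary. Section 11.2.5 adds compliance questions at each visit and diary tracking, so a missed day would at least be recorded. All of this stands, and it is why the point is minor. It does not make the form right. For a Day -6 starter the five-day reminder contradicts the Day -2 row in the same diary, and that row has no morning or evening time fields in which to record a fifth day.

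A reader might infer that the shortfall arises under any day numbering. The documents do not support that. Some sections use a Day 0; the biopsy timing in section 3.1.2, for example, is "on the day of or the day before the start of eribulin (day -2 to day 0". If Day 0 is a separate day before Day 1, reaching a count of 4 requires matching a label that counts Day 0 to a diary that has none. That would leave 6 diary days (-6 to -1) to cover 7 calendar days. The finding therefore rests on the diary's own numbering.

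A reader might also infer that section 11.2.1 contradicts sections 3.1.2 and 5.1, because 5 + 2 = 7 days does not fit a 6-day lead-in. That goes too far. The mismatch disappears if a Day 0 precedes Day 1. In any case, the specific lead-in rule, stated twice, governs over a general description of the weekly schedule. At most, the wording of section 11.2.1 is loose.

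**Conclusion.** The point holds as a minor inconsistency between a patient form and the protocol. In the diary's numbering, a Day -6 starter who follows the labelled rows would take 4 lead-in dosing days instead of 5, which is 800 mg or 20% less.

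This rests on three assumptions: that there is no separate Day 0 in the diary's count, that some patients start on Day -6, and that such a patient follows the labels without being redirected. The documents do not give the number of Day -6 starters, so the number affected may be anything from none upward.

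The reach is limited to lead-in exposure and the comparisons of CSF1, leukocytes and tissue before eribulin, which section 12.7 (Correlative studies) treats as exploratory. The primary endpoint is timed from the first combined administration (section 12.2). Neither it, nor the sample size, nor the stopping rules are affected.

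**What to change.** Add a Day -6 lead-in layout to the Phase II diary: dosing on Days -6 to -2 with morning and evening fields, and no drug on Day -1. That gives 5 + 1 = 6 days and 4000 mg, as sections 3.1.2 and 5.1 require. Alternatively, put a note on the Day -2 row saying that patients who started on Day -6 take their fifth day of drug then and have only Day -1 off, with space to record times and capsules.

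In either case, state that the diary's Day -1 is the day immediately before eribulin Day 1, with no Day 0 between them.

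The cost is one extra grid or one note on a form. No visit, sample or patient is added, and both start days can stay.
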